# A Phase 2 Study of Clofarabine, Idarubicin, Cytarabine, Vincristine, and Corticosteroids for Patients with Newly Diagnosed or Relapsed Mixed Phenotype Acute Leukemia

## I. Objectives

Primary:

To evaluate the response rate of the chemotherapy regimen in patients with mixed phenotype acute leukemia

Secondary:

To evaluate the durability of response, the overall and event-free survival rates, and the safety profile of the regimen

#### II. Rationale

The diagnosis of acute leukemia is typically based on an evaluation of the morphology, immunophenotype, karyotype, and molecular features of blast cells found in the bone marrow. Most often, the leukemia is clearly assigned to one of the following specific lineages: B-lymphoid, T-lymphoid, or myeloid. Diagnosis is usually unequivocally acute myeloid leukemia (AML), or acute lymphoid leukemia (ALL). ALL is further delineated into B- or T-cell groups. The therapeutic regimen is often designed based on the lineage of the leukemia. Nevertheless, rarely a patient cannot be readily classified due to immunophenotypic evidence of multiple lineages within the cell population [1]. Throughout the years, these leukemias have been referred to by a number of names, including mixed lineage leukemia, biphenotypic leukemia, bilineal leukemia, hybrid leukemia, undifferentiated leukemia, or leukemia of ambiguous lineage. This terminology has been used to describe leukemias with a single population of cells expressing markers from multiple lineages, as well as leukemias exhibiting two distinct blast populations each belonging to a distinct lineage. In 2008, the World Health

Organization (WHO) grouped these processes together under the heading mixed phenotype acute leukemia (MPAL) [2].

The definition of MPAL has evolved over the years, but most now accept the WHO definition published in 2008 [2]. Briefly, a blast population is myeloid if there is sufficient present of myeloperoxidase (MPO) or monocytic differentiation is present. The T lineage is defined by the presence of cytoplasmic or surface CD3. To assign the B lineage, a combination of the expression of several markers is used, including CD19, CD79a, CD22, and CD10.

There is no standard therapy for the group of patients diagnosed with MPAL, and the situation presents a clinical challenge that has not been well studied. Most experience to date comes from the pediatric literature and from older case series. Killick and colleagues identified 25 cases of "biphenotypic" leukemia of 693 cases (3.6%) of acute leukemia over an 8 year period [3]. This cohort included pediatric patients as young as 3 years of age, and adults up to age 46. A wide variety of induction regimens were used, including conventional ALL induction, conventional AML induction, as well regimens that used agents typically used to treat both lineages. Median overall survival (OS) for the 20 de novo patients was 27.3 weeks, which is very poor considering a median age of 25.5 years. Importantly, several patients also had the Philadelphia chromosome, and treatment was before the era of tyrosine kinase inhibitors.

Recently, a group from Saudi Arabia described the clinical characteristics and outcome of 24 pediatric patients diagnosed with MPAL [4]. All patients were treated uniformly with a modified St. Jude Total Therapy-B HR regimen, which that group uses to treat high risk ALL [5]. This regimen involves at least six drugs with activity against lymphoid and myeloid leukemias. All patients were also considered for allogeneic stem cell transplantation (alloSCT) in first complete remission (CR). For patients not undergoing alloSCT, maintenance therapy was continued for 2.5 years. With a median follow up of four years, the survival was 75.7%, which is excellent, but must be interpreted keeping

in mind that the median age was 8.7 years. AlloSCT did not improve the outcome in this small study.

The St. Jude's Children's Research Hospital has recently published their own experience treating pediatric patients with mixed lineage acute leukemias [6]. Thirty-five patients were treated, and the median age was 10. Overall, 23 patients received AML induction (daunorubicin, cytarabine, etoposide), and 12 received standard ALL induction (vincristine, daunorubicin, L-asparaginase, prednisone). Patients receiving AML or ALL induction regimens up front achieved CR rates of 52% and 83%, respectively. Eighty percent of the patients not achieving CR after AML induction subsequently went into CR after ALL induction. The 5-year OS for patients with B/Myeloid or T/Myeloid was 47.8%.

There is very little reported in the literature on adults with MPAL, and as a referral center, we may encounter these patients more often that other institutions. A contemporary regimen employing drugs active against both myeloid and lymphoid leukemias may be the optimal approach. AML is generally treated with anthracyclines combined with cytarabine [7-9]. Recently, the addition of a cladribine, a purine analog, to standard AML induction improved the survival of younger patients with newly diagnosed disease [10]. Clofarabine is also a purine analog that was rationally designed to optimize the pharmacologic shortcomings of two of its predecessors, fludarabine and cladribine [11]. The drug works through several mechanisms including inhibition of deoxyribonucleic acid (DNA) polymerases, inhibition of ribonucleotide reductase, and induction of apoptosis via DNA strand breaks and disruption of mitochondrial integrity [11]. Clofarabine is currently approved for pediatric patients with relapsed and refractory acute lymphoid leukemia after failure of two previous regimens [12]. When administered three to six hours prior to cytarabine, in vitro both drugs induce a synergistic effect against AML cells, possibly due to the ability of clofarabine to efficaciously block ribonucleotide reductase [13]. These data have formed the basis for several clinical studies that we and others have conducted in an attempt to exploit this relationship, and hence, improve AML outcomes [14]. Currently, our frontline AML induction regimen of choice is a combination of clofarabine, cytarabine, and idarubicin.

The frontline strategy for the management of adult ALL is similar to pediatrics, and involves induction chemotherapy, multiple rounds of consolidation, a prolonged maintenance phase, as well as central nervous system (CNS) prophylaxis. Most protocols call for approximately 3 years of therapy in total. There are several accepted regimens employed in the United States, and most involve the same key agents which include vincristine, anthracycline (e.g., doxorubicin or daunorubicin), corticosteroids (e.g., prednisone or dexamethasone), with or without some form of L-asparaginase [15-17]. One such regimen is the hyperCVAD, which employs the combination of hyperfractionated cyclophosphamide, vincristine, doxorubicin, and dexamethasone alternating with high dose methotrexate and cytarabine [18, 19]. Cycles are repeated approximately monthly for 8 cycles, a point at which patients move to the maintenance portion of the regimen with daily mercaptopurine, monthly vincristine, weekly methotrexate, and monthly pulses of prednisone (POMP). Long term outcomes have been published previously, with five year overall survival (OS) of 38%. Survival was influenced by several prognostic factors that were assessed using multivariable analysis. This is comparable to a number of other regimens that are used depending on center preference.

At the M.D. Anderson Cancer Center (MDACC), MPAL has traditionally been treated with AML induction regimens. It may be optimal to also administer agents that are predominantly used against ALL. Therefore, we are proposing to use a hybrid regimen, with components of both AML and ALL therapy, to treat patients diagnosed with MPAL at MDACC. The backbone of the regimen will be our standard induction for AML, clofarabine, idarubicin, and cytarabine administered at attenuated doses. Importantly, all three of these drugs also have activity against ALL. In addition, we will add vincristine and corticosteroids to the regimen for enhanced lymphoid activity. These are ideal candidates for addition to the regimen for a number of reasons. First, the toxicity profiles do not overlap, allowing us to safely give all five agents during the same course of therapy. Second, corticosteroids are routinely used as a premedication to prevent toxicity induced by moderate to high doses of cytarabine, albeit at lower doses.

# **III. Background Drug Information**

All drugs used in this protocol are available commercially

#### A. Idarubicin:

Idarubicin is commercially available.

#### Mechanism of action:

Similar to doxorubicin and daunorubicin; inhibition of DNA and RNA synthesis by intercalation between DNA base pairs.

#### **Adverse effects:**

- Cardiovascular: Transient EKG abnormalities (supraventricular tachycardia, S-T wave changes, atrial or ventricular extrasystoles); generally asymptomatic and self-limiting. Congestive heart failure, dose-related. The relative cardiotoxicity of idarubicin compared to doxorubicin is unclear. Some investigators report no increase in cardiac toxicity at cumulative oral idarubicin doses up to 540 mg/m²; other reports suggest a maximum cumulative intravenous dose of 150 mg/m².
- Central nervous system: Headache
- Dermatologic: Alopecia (25% to 30%), radiation recall, skin rash (11%), urticaria
- Gastrointestinal: Nausea, vomiting (30% to 60%); diarrhea (9% to 22%); stomatitis
   (11%); GI hemorrhage (30%)
- Genitourinary: Discoloration of urine (darker yellow)

# B. Cytarabine

Cytarabine is commercially available.

#### Mechanism of action:

Cytarabine is an antimetabolite. Cytarabine is cell cycle–specific for the S phase of cell division. Activity occurs as the result of activation to cytarabine triphosphate in the tissues and includes inhibition of DNA polymerase and incorporation of cytarabine into DNA and RNA.

#### Adverse effects:

#### COMMON

· Cardiovascular: Thrombophlebitis

• Dermatologic: Rash, conjunctivitis

• Endocrine metabolic: Hyperuricemia

• Gastrointestinal: Anal inflammation, Diarrhea, Loss of appetite, Nausea, Stomatitis, Ulcer of anus, Ulcer of mouth, Vomiting

• Hematologic: Decreased reticulocyte count, Megaloblastic anemia

Hepatic: Decreased liver function

Other: Fever

#### **SERIOUS**

• Hematologic: Anemia, Bleeding, Leukopenia, Thrombocytopenia

7

• Immunologic: Anaphylaxis

Neurologic: Neuropathy

• Renal: Kidney disease

• Other: Infectious disease, Sepsis

#### C. Clofarabine

Clofarabine is commercially available.

#### Mechanism of action:

Clofarabine potently inhibits DNA synthesis by inhibiting both DNA polymerase and ribonucleotide reductase. Clofarabine demonstrated the ability to disrupt mitochondrial integrity that results in the release of pro-apoptotic proteins, cytochrome C and apoptosis-inducing factor.

#### Adverse effects:

- Hematologic: Myelosuppression, infections
- Hepato and Gastrointestinal: Nausea/vomiting, diarrhea, mucositis, stomatitis/pharyngitis, hyperbilirubinemia, increase of SGPT and/or SGOT, abdominal pain or cramping, peritonitis, pancreatitis, liver failure
- Dermatologic: Skin rash with blisters (particularly hand-foot syndrome), Steven-Johnson's syndrome, alopecia, conjonctivitis
- Systemic: Fatigue, asthenia, anorexia, lethargy, malaise, mental status changes/coma, alopecia
- Allergic reactions: (including fever, muscle aches, edema, dyspnea)
- Cardiology: Congestive heart failure

- Nephrology: Kidney failure
- Autoimmune reactions: (antiplatelet antibodies, erythema nodosum) and/or chemical imbalances in the blood.

#### D. Vincristine

Vincristine is commercially available

#### **Mechanism of Action**

Binds to tubulin and inhibits microtubule formation; therefore arresting the cell at metaphase by disrupting the formation of the mitotic spindle. It is specific for the S and M phases of the cell cycle.

#### **Adverse Effects**

- Peripheral neuropathy
- Constipation
- Ileus
- Loss of deep tendon relexes
- Wrist and foot drop
- Hyponatremia
- Convulsions (rare)
- Severe soft tissue damage if extravasated
- Alopecia
- Paresthesia

#### E. Dexamethasone and Prednisone

Dexamethasone and prednisone are commercially available

#### Mechanism of action

Decreases inflammation by suppression of neutrophil migration. In leukemia cells, induces cell cycle arrest and apoptosis.

#### **Adverse Effects**

- Salt or fluid retention
- Hypertension
- Muscle weakness or loss of muscle mass
- Osteoporosis
- Aseptic necrosis of the heads of femur or humerus
- Peptic Ulcer
- Pancreatitis
- Skin fragility
- Acute psychosis (rare)
- Elevated blood sugar
- Increased intraocular pressure

#### F. Methotrexate

Methotrexate is commercially available

#### **Mechanism of Action**

Methotrexate is a folate antimetabolite that inhibits DNA synthesis. Methotrexate irreversibly binds to dihydrofolate reductase, inhibiting the formation of reduced folates, and thymidylate synthesis, resulting in inhibition of purine synthesis.

#### Adverse Effects

- Myelosuppression
- Anorexia

- Mucositis
- Alopecia
- Rash
- Photosensitivity
- Infertility
- Interstitial pneumonitis
- Renal failure
- Hepatic dysfunction
- Leukoencephalopathy
- Menstrual dysfunction

## G. 6-Mercaptopurine

6-Mercaptopurine is commercially available

## **Mechanism of Action**

Purine antagonist which inhibits DNA and RNA synthesis; acts as false metabolite and is incorporated into DNA and RNA, eventually inhibiting their synthesis.

## **Adverse Effects**

- Myelosuppression
- Liver failure
- Diarrhea
- Rash
- Nausea and vomiting

#### H. Rituximab

Rituximab is commercially available

#### **Mechanism of Action**

Rituximab is a monoclonal antibody that binds to the CD20 cell surface antigen. Binding of rituximab leads to antibody-dependent cellular cytotoxicity as well as complement mediated cytotoxicity.

## **Adverse Effects**

- Infusion reactions (fever, chills, rigors, hypotension, tachycardia, shortness of breath)
- Reactivation of hepatitis B
- Dermatologic reactions
- Lymphopenia

# IV. Eligibility Criteria

#### **Inclusion Criteria**

- 1. Sign an informed consent document
- 2. Age 18 >/= 18
- 3. Newly diagnosed or relapsed MPAL, which for this protocol, will be defined as follows:
- -Bone marrow result interpreted by the reading Pathologist (or tissue biopsy for cases of extramedullary disease) as: biphenotypic leukemia, bilineal leukemia, undifferentiated leukemia, mixed lineage leukemia, leukemia of ambiguous lineage, T/Myeloid leukemia, B/Myeloid leukemia, or other diagnosis indicating the presence of multiple lineages within the cell population.

Or

- -Immunophenotype consistent with WHO definition of MPAL
- 4. ECOG Performance Status of ≤ 3 at study entry.
- 5. Adequate organ function as outlined below (unless due to leukemia)
  - Serum creatinine ≤ 3 mg/dL
  - Total bilirubin ≤ 2.5 mg/dL
  - ALT (SGPT) and/or AST (SGOT) ≤ 3 x ULN or ≤ 5 x ULN if related to disease
- 6. Women of childbearing potential must have a negative serum or urine pregnancy test within 7 days. Women of childbearing potential and men must agree to use contraception at study entry and for the duration of active study treatment.
- Cardiac ejection fraction ≥ 40% (by either cardiac echo or MUGA scan).
   Documentation of recent (≤ 6 months from screening) outside reports is acceptable.
- 8. If newly diagnosed, prior therapy with hydrea and/or steroid and the use of a single or a two day dose of cytarabine (up to 3 g/m²), for emergency use up to 24 hours prior to start of study therapy is allowed.

#### **Exclusion Criteria**

- 1. Breast feeding females
- 2. Patients with active, uncontrolled infections
- 3. Patients with active secondary malignancy will not be eligible unless approved by the Principal Investigator.

#### V. Treatment Plan

## 1. Study Design

This will be a phase II, single center, open label trial to assess the safety and efficacy of the regimen outlined below. Patients will be eligible if they are newly diagnosed or with relapsed disease, though these groups will be analyzed separately. We anticipate enrolling 10 – 20 patients per year.

All drugs will be given using commercial supply. For patients over the age of 80 years, further dose decrease beyond what is stated below is allowed at the discretion of the treating physician and if felt in the best interest of the patient.

#### 2. Induction

- Clofarabine 15 mg/m² IV daily over approximately 60 minutes for 4 days on days
   1 4 (for 3 days on days 1-3 for patients 61 80 years of age or with
   performance status (PS) of 2 or 3)
- Idarubicin 10 mg/m² IV over approximately 30 60 minutes daily for 3 days on days 1 3 (for 2 days on days 1-2 for patients 61-80 years of age or with PS 2 or 3)
  - To start 1 2 hours after the clofarabine
- Cytarabine 1,000 mg/m² IV over approximately 2 hours daily for 4 days on days 1
   4 (for 3 days on days 1-3 for patients 61 80 years of age or with PS 2 or 3)
  - To start 3 6 hours after the clofarabine

- Vincristine 2 mg (FLAT dose) IV over approximately 15 30 minutes on days 1,
   8, and 15
- Dexamethasone 40 mg IV daily for 4 days on days 1 4 and days 15 18
  - May be given 30 60 minutes prior to each dose of cytarabine during induction on days 1 – 4 (if rituximab given, can administer dexamethasone prior to rituximab on day 1)

For patients with CD20 positive disease (≥ 10% of the lymphoid population), rituximab may be added to the regimen as follows:

- Rituximab 375 mg/m^2 IV infused according to package labeling on days 1 and 8.
  - Rituximab will be infused according to the package insert. Premedications
    will be administered according to departmental standard/prescribing
    information to prevent infusion related reactions.

The doses and schedule can be modified for the following situations:

- For patients 61 80 years of age or with performance status of 2 or 3: give clofarabine and cytarabine for 3 days; give idarubicin for 2 days as mentioned above.
- Further dose reductions or modifications can be considered after discussion with the PI and the discussion documented in the patient's medical record

- All patients will receive at least one lumbar puncture during the first cycle of induction. This is for diagnosis as well as for the application of prophylactic intrathecal chemotherapy (methotrexate 12 mg or cytarabine 100 mg).
- The standard for ALL patients is to administer 8 prophylactic intrathecal chemotherapy treatments during induction and consolidation. Methotrexate is alternated with cytarabine, and patients typically receive two treatments per cycle for the first four cycles.
- For this protocol, giving more than one intrathecal treatment will be at the discretion of the managing physician. This degree of flexibility is warranted due to the heterogeneity of patients with MPAL.

Patients, who have not achieved a complete remission (CR)/complete remission without platelet (CRi) recovery following one induction course can receive a second induction course to optimize response if possible. A second induction course at the same dose as the previous course or in a dose-reduced fashion should not be given until at least 28 days of course 1. If the bone marrow aspirate and/or biopsy(s) performed after the reinduction cycle reveals a remission marrow (CR/CRi), then the patient may proceed with consolidation at the discretion of the treating investigator. In addition, any clinically significant drug-related, non-hematologic toxicity experienced by a patient should return to ≤ grade 2 or the baseline grade before the patient continues treatment. Should the patient not have achieved a remission, including CR and CRi after the re-induction course, he/she will be taken off study for failure to respond, unless the patient has

achieved clinical benefit or partial remission, at which time further therapy on protocol may be permitted with approval from the PI.

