## 3. Consolidation

Patients in CR or CRi can continue with up to 6 consolidation cycles.

- Clofarabine 15 mg/m² IV daily over approximately 60 minutes for 3 days on days
   1 3 (for 2 days on days 1-2 in patients 61 80 years of age or with PS 2 or 3)
- Idarubicin 6 mg/m² IV over 30 60 minutes daily for 2 days on days 1 2 (3
   mg/m² for 2 days on days 1-2 in patients 61-80 years of age or with PS 2 or 3)
  - To start 1 2 hours after the clofarabine
- Cytarabine 1,000 mg/m² IV over approximately 2 hours daily for 3 days on days
   1 3 (for 2 days on days 1-2 in patients 61 80 years of age or with PS 2 or 3)
  - To start 3 6 hours after the clofarabine
- Vincristine 2 mg (FLAT dose) IV over 15 30 minutes on days 1, 8, and 15
- Dexamethasone 40 mg IV daily for 4 days on days 1 4 and days 15 18
  - May be given 30 60 minutes prior to each dose of cytarabine during consolidation on days 1 – 3 (if rituximab given, can administer dexamethasone prior to rituximab on day 1)

For patients with CD20 positive disease ( $\geq$  10% of the lymphoid population), rituximab may be added to the regimen as follows during consolidation cycles 1 – 3:

• Rituximab 375 mg/m² IV infused according to package labeling on days 1 and 8

Rituximab will be infused according to the package insert. Premedications
will be administered according to departmental standard/prescribing
information to prevent infusion related reactions.

The doses and schedule can be modified for the following situations:

- For patients 61 80 years of age or with performance status of 2 or 3: give clofarabine and cytarabine for 2 days; give idarubicin 3 mg/m² for 2 days as mentioned above.
- Further dose reductions can be considered after discussion with the PI

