#### 4. Dose Modifications

Drug doses in subsequent consolidation cycles may be modified for clinically significant drug-related > grade 2 non-hematologic toxicities. Dose reductions can also be made in other clinical situations where this step is considered to be in the best interest for the patient and after discussion with the principal investigator and the discussion documented in the patient's medical record. Doses of each individual drug can be modified if a toxicity is considered due this particular drug.

The following are suggestions for dose modifications in subsequent treatment courses:

- Persistent neutropenia (< 1,000) or thrombocytopenia (< 50,000) greater than 42 days from previous cycle: reduce doses of clofarabine, cytarabine and idarubicin by 20 25%

- Clinically significant peripheral neuropathy persisting for > 2 weeks:
  - 50% reduction of vincristine (1 mg) for Grade 2 persistent neuropathy
  - Eliminate vincristine for Grade 3-4 neuropathy, seizures and Ileus suspected to be related to vincristine

Organ specific dose adjustments:

	Cytarabine	Idarubicin	Clofarabine	Vincristine
Serum Creatinine (mg/dL)				
2.1 – 3	75% of current dose	75% of current dose	75% of current dose	100% of current dose
Above 3	Discuss with PI			
Bilirubin (mg/dL)				
2 – 3	100% of current dose	75% of current dose	100% of current dose	50% of current dose or omit
3.1 – 5	100% of current dose	50% of current dose	Discuss with PI	Omit
Above 5	100% of current dose	Omit	Discuss with PI	Omit

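### The reduced chemotherapy schedule stops at age 80 although eligibility has no upper age, so fit patients aged 81 or older default to the full dose

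*Combined protocol and SAP*

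**What the plan says.** Section IV sets a minimum age of 18. It gives no maximum, and the exclusion criteria have no age item. Performance status is limited only by "ECOG Performance Status of ≤ 3 at study entry", so a patient over 80 with PS 0-1 can enrol.

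Section V.2 (Induction) gives each of the three main cytotoxic drugs a full and a reduced schedule. For idarubicin the reduced one applies "for 2 days on days 1-2 for patients 61-80 years of age or with PS 2 or 3". The clofarabine and cytarabine lines use the same trigger, and a modification bullet repeats it. Section V.3 (Consolidation) follows the same pattern, for example "for 2 days on days 1-2 in patients 61 80 years of age or with PS 2 or 3" (the extracted text has lost the dash in the age range here; the idarubicin lines print it intact).

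Patients over 80 are mentioned once, in V.1 (Study Design): "For patients over the age of 80 years, further dose decrease beyond what is stated below is allowed at the discretion" of the treating physician. Other reductions are open to patients of any age after discussion with the principal investigator (PI), in V.2, V.3 and V.4. The V.4 wording is "Dose reductions can also be made in other clinical situations where this step is considered to be in the best interest for the patient".

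**The concern.** The protocol reduces dose for age alone from 61 onward, even in patients with PS 0-1, and then stops doing so at 81 without giving a reason. Read as written, the oldest fit patients have a higher default dose than patients aged 61-80. The V.1 sentence points the other way: a *further* decrease makes most sense for patients who already start from a reduced schedule, and the age bands do not give patients over 80 with PS 0-1 that start.

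The starting dose for this group therefore depends on whether a physician uses an optional sentence placed outside the dosing lines. Two similar 82-year-olds could receive clearly different doses and both be treated per protocol. The drugs are myelosuppressive, and the protocol lists congestive heart failure for idarubicin and clofarabine. The early-death and toxicity stopping rules in section XI would not reveal the problem, because their boundaries start at 10 patients and none is specific to age.

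**Working it through.** **Who gets which schedule.** The trigger for the reduced schedule is age 61-80 or PS 2-3. It is stated in eight places: the clofarabine, idarubicin and cytarabine lines and one modification bullet in V.2, and the same four in V.3.

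| Patient | Age trigger met | PS trigger met | Default schedule |
|---|---|---|---|
| Age 61-80, PS 0-1 | yes | no | reduced |
| Age 61-80, PS 2-3 | yes | yes | reduced |
| Age 81+, PS 2-3 | no | yes | reduced |
| Age 81+, PS 0-1 | no | no | full |

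Only the last group is affected.

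**Dose per course.** Inputs are the daily doses and day counts in V.2 and V.3. Total = daily dose × days, in mg/m².

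| Course | Drug | Full (81+, PS 0-1) | Reduced (61-80, PS 0-1) | Excess |
|---|---|---|---|---|
| Induction | clofarabine | 15 × 4 = 60 | 15 × 3 = 45 | +33% |
| Induction | idarubicin | 10 × 3 = 30 | 10 × 2 = 20 | +50% |
| Induction | cytarabine | 1,000 × 4 = 4,000 | 1,000 × 3 = 3,000 | +33% |
| Consolidation cycle | clofarabine | 15 × 3 = 45 | 15 × 2 = 30 | +50% |
| Consolidation cycle | idarubicin | 6 × 2 = 12 | 3 × 2 = 6 | +100% |
| Consolidation cycle | cytarabine | 1,000 × 3 = 3,000 | 1,000 × 2 = 2,000 | +50% |

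**Whole treatment, upper bound.** V.3 states "Patients in CR or CRi can continue with up to 6 consolidation cycles". With one induction and six consolidations:
- clofarabine: 60 + 6 × 45 = 330 against 45 + 6 × 30 = 225 (+47%)
- idarubicin: 30 + 6 × 12 = 102 against 20 + 6 × 6 = 56 (+82%)
- cytarabine: 4,000 + 6 × 3,000 = 22,000 against 3,000 + 6 × 2,000 = 15,000 (+47%)

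V.2 also says that patients not in remission after the first course "can receive a second induction course to optimize response if possible". With a second induction at the same dose:
- clofarabine: 120 + 270 = 390 against 90 + 180 = 270 (+44%)
- idarubicin: 60 + 72 = 132 against 40 + 36 = 76 (+74%)
- cytarabine: 8,000 + 18,000 = 26,000 against 6,000 + 12,000 = 18,000 (+44%)

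For scale, the idarubicin background in section III.A notes that "other reports suggest a maximum cumulative intravenous dose of 150 mg/m²". The full-schedule total is 132/150 = 88% of that figure and the reduced total is 76/150 = 51%. Neither exceeds it.

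**Number affected.** Maximum enrolment is 40 newly diagnosed plus 20 relapsed patients, 60 in all (section XI, Parts I and II). The documents give no age distribution. If 0-5% were over 80 with PS 0-1 (an assumption), that is 0 to 0.05 × 60 = 3 patients.

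**The case against.** The protocol does not ignore patients over 80. V.1 names them before the dosing lines and lets the treating physician reduce the dose without PI approval. Other sections allow PI-discussed reductions for anyone. What is missing is a starting dose, not all protection. This is correct, and many physicians would probably reduce. But every one of these routes is a permission, and none sets a starting dose for this group.

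The V.1 wording could also be read differently. It is literally true for patients over 80 with PS 2-3, who do have a reduced schedule, and it could simply mean decreases larger than any the protocol lists. The view that the authors meant everyone over 80 to start from the reduced schedule is therefore probable rather than certain. Neither alternative removes the inversion: the sentence covers all patients over 80, and under any reading it only permits a decrease.

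Two of the eight statements of the reduced schedule, the modification bullets, sit under a permissive heading, so the 61-80 rule is itself not wholly rigid. The six drug lines are firmer and are what a prescriber would follow.

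Finally, the whole-treatment totals are a stacked worst case. The second induction may be given at a lower dose, six consolidation cycles is a maximum, and toxicity rules would often intervene. The 150 mg/m² figure is a literature remark, not a protocol limit. This stands: the per-course differences are the more informative measure, and the totals are upper bounds only.

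**Conclusion.** The concern holds. By the stated rule, a patient aged 81 or older with PS 0-1 falls on the full schedule, while a patient aged 61-80 with the same PS gets the reduced one. Per induction course the default is higher by a third for clofarabine and cytarabine and by half for idarubicin. Per consolidation cycle it is higher by half for clofarabine and cytarabine and doubled for idarubicin. These figures assume that no discretion is used.

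This is most likely a drafting gap. The textual finding is firm, but the practical effect is probably small because few such patients are expected and a physician may reduce the dose. No stopping boundary, operating characteristic or other statistical figure is affected. It should still be corrected, because it sets an inverted default dose of cytotoxic drugs for the oldest patients and the correction is simple.

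**What to change.** Change the age band to 61 years of age or older in all eight places: the three drug lines and the modification bullet in V.2, and the same four in V.3. Keep the physician's discretion in V.1, reworded so that for patients over 80 it is a further decrease from the reduced schedule. An upper age limit is not needed.

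Per induction course, the default for patients aged 81+ with PS 0-1 would fall by 25% for clofarabine (60 to 45 mg/m²), 33% for idarubicin (30 to 20) and 25% for cytarabine (4,000 to 3,000). Per consolidation cycle it would fall by 33%, 50% and 33%.

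The cost is a wording amendment at eight places plus one sentence, with no added procedures, patients or statistical work. The one downside is that a fit patient over 80 would no longer receive the full schedule by default, which is how the protocol already treats fit patients aged 61-80.
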